5.1.3 FACS Analyses

FACS analyses of CD4⁺, CD8⁺, NK cells and T-cell central and effector memory subsets will also be assessed at the same time the patient's ATL count is assessed to explore the effects of ruxolitinib on the immune effector cells. **NOTE:** Flow cytometry samples to assess lymphocyte sets and subsets will also be sent to Flow Cytometry/Immunology Laboratory Department of Laboratory Medicine for the Clinical Center (Section 3.4.1.6).

5.1.4 Analysis of STAT5; phosphoSTAT5 and serum ruxolitinib level

NOTE: These samples are optional and will be collected at the discretion of the PI. When collected, the following applies:

If sufficient numbers of ATL cells are obtained from the PBMC samples drawn for the proliferation assays, the cellular lysates will also be used to perform the intracellular FACS analyses for expression of STAT 5 and phosphoSTAT5 or other proteins of interest associated with the JAK-STAT pathway. When samples are collected independently of time points for PBMC samples for in vitro proliferation assays (e.g., Cycle 1 Day 1 post-treatment), blood will be drawn in a heparinized (green top) tubes. For these analyses, about 30 mL of blood is anticipated to be needed; however, may be adjusted based upon the number of cells collected and ongoing assay development with observation of the maximum amount of blood allowed to be collected within any 8-week period.

A serum sample will also be collected at each of the same time points (5 mL SST tubes) and retained to allow for comparison of ruxolitinib level to STAT5 and phosphoSTAT5 measurements.

5.1.5 Molecular Analysis for T-cell Receptor Gamma (TCR γ) Gene Rearrangement

To detect clonality and analysis of HTLV-1 viral titer, blood will be collected in light blue (citrate buffer) tubes (4 mL). The blood will be transported to [name] attention to [name] or designee. These samples will be stored at -70° C until batch analysis is performed.

5.1.6 Optional Tumor Biopsies

Patients with easily accessible tumor deposits who consent to this procedure will have a fine-needle aspiration or punch biopsy of one of their tumors at baseline and during the first 28 days of treatment (between days 14 through 28) to assess for changes in their ATL infiltration and changes in gene expression associated with ruxolitinib treatment. Patients who consent to additional optional FNA's may be asked to undergo an FNA during the study treatment and/or if they have progressive disease while on-study. These biopsies will help us gain additional insight into the *in vivo* effects of ruxolitinib. These samples will be used for research. A 23-gauge hypodermic needle will be used to obtain biopsies from the tumor mass. After insertion, multiple passes at changing angles of insertion will be made through all quadrants of the tumor. Alternatively, standard punch biopsy technique will be followed.

5.2 SAMPLE STORAGE, TRACKING AND DISPOSITION

Samples will be ordered in CRIS and tracked through a Clinical Trial Data Management system. Should a CRIS screen not be available, the CRIS downtime procedures will be followed. Samples will not be sent outside NIH without appropriate approvals and/or agreements, if required.

All specimens obtained in the protocol are used as defined in the protocol. Any specimens that are remaining at the completion of the protocol will be stored in the conditions described below. The

study will remain open so long as sample or data analysis continues. Samples from consenting patients will be stored until they are no longer of scientific value or if a subject withdraws consent for their continued use, at which time they will be destroyed.

If the patient withdraws consent his/her data will be excluded from future distributions, but data that have already been distributed for approved research use will not be able to be retrieved. The PI will record any loss or unanticipated destruction of samples as a deviation. Reporting will be per the requirements of section [7.2.1](#).

5.2.1 Research Sample Control

- For research samples obtained for investigation, the Clinical Support Laboratory, Leidos Biomedical Research, Inc.-Frederick processes and cryopreserves samples in support of IRB-approved, NCI clinical trials. The laboratory is located in a controlled-access building and laboratory doors are kept locked at all times. Upon specimen receipt, each sample is assigned a unique, sequential laboratory accession ID number. All products generated by the laboratory that will be stored either in the laboratory freezers or at a central repository facility are identified by this accession ID. An electronic database is used to store information related to patient samples processed by the laboratory. Vial labels do not contain any personal identifier information. Samples are stored inventoried in locked laboratory freezers and are routinely transferred to the NCI-Frederick repository facilities for long-term storage. These facilities are operated under subcontract to Leidos Biomedical Research, Inc.-Frederick. Access to stored clinical samples is restricted. Investigators establish sample collections under “Source Codes” and the investigator responsible for the collections, typically the protocol Principal Investigator, specifies who has access to the collection.
- When requests are submitted by the NCI investigator for shipment of samples outside of the NIH, it is the policy of the laboratory to request documentation that appropriate approvals and/or agreements, if required, are in place that covers the specimen transfer. The laboratory does not provide patient identifier information as part of the transfer process but may, at the discretion of the NCI investigator, group samples from individual patients when that is critical to the testing process. The NCI investigator responsible for the sample collection is responsible for ensuring appropriate approvals and/ or agreements are in place prior to requesting the laboratory to ship samples outside of the NIH.
- Blood and tissue specimens collected in the course of this research project may be banked and used in the future to investigate new scientific questions related to this study. However, this research may only be done if the risks of the new questions were covered in the consent document and the proposed research has undergone prospective IRB review and approval. If new risks are associated with the research (e.g., analysis of germline genetic mutations), the Principal Investigator must amend the protocol and obtain informed consent from all research subjects.
- Once primary research objectives for the protocol are achieved, intramural researchers can request access to remaining samples provided they have an IRB-approved protocol and patient consent. Access to these samples will only be granted following IRB approval of an additional protocol, granting the rights to use the material.

5.2.2 Tracking

- All samples will be barcoded, with data entered and stored in the Labmatrix Data Management System utilized by the Lymphoid Malignancies Branch. This is a secure program, with access to this system limited to defined MB personnel, who are issued individual user accounts. The program creates a unique barcode ID for every sample and sample box, which cannot be traced back to patients without Labmatrix access. The data recorded for each sample includes the patient ID, name, trial name/protocol number; time drawn, cycle time point, dose, material type, as well as box and freezer location. Patient demographics associated with the Clinical Center patient number are provided in the system. For each sample, there are notes associated with the processing method (delay in sample processing, storage conditions on the ward, etc.).
- Barcoded samples are stored in barcoded boxes in a locked freezer at either -20°C or -80°C according to stability requirements. These freezers are located onsite in the Clinical Support Laboratory and offsite at NCI-Frederick Central Repository Services in Frederick, MD. Samples will be stored until requested by a researcher named on the protocol. All requests are monitored and tracked in the Labmatrix System. All researchers are required to sign a form stating that the samples are only to be used for research purposes associated with this trial (as per the IRB-approved protocol) and that any unused samples must be returned to the Clinical Support Laboratory.
- Sample barcodes are linked to patient demographics and limited clinical information. This information will only be provided to investigators listed on this protocol, via registered use of the Labmatrix System.

6 DATA COLLECTION AND EVALUATION

6.1 DATA COLLECTION

The PI will be responsible for overseeing entry of data into an in-house password protected electronic system (C3D) and ensuring data accuracy, consistency and timeliness. The principal investigator, associate investigators/research nurses and/or a contracted data manager will assist with the data management efforts. All data obtained during the conduct of the protocol will be kept in secure network drives or in approved alternative sites that comply with NIH security standards. Primary and final analyzed data will have identifiers so that research data can be attributed to an individual human subject participant.

All adverse events, including clinically significant abnormal findings on laboratory evaluations, regardless of severity, will be followed until return to baseline or stabilization of event. AEs will be documented from the first study intervention, through 30 days following the last dose of study agent. Beyond 30 days after the last intervention, only adverse events which are serious and related to the study intervention need to be recorded

End of study procedures: Data will be stored according to HHS, FDA regulations, and NIH Intramural Records Retention Schedule as applicable.

Loss or destruction of data: Should we become aware that a major breach in our plan to protect subject confidentiality and trial data has occurred, this will be reported expeditiously per requirements in section [7.2.1](#).

6.1.1 Data Collection/Recording Exceptions

6.1.1.1 Abnormal Laboratory Values

An abnormal laboratory value will be recorded in the database as an AE **only** if the laboratory abnormality is characterized by any of the following:

- Results in discontinuation from the study
- Is associated with clinical signs or symptoms
- Requires treatment or any other therapeutic intervention
- Is associated with death or another serious adverse event, including hospitalization.
- Is judged by the Investigator to be of significant clinical impact
- If any abnormal laboratory result is considered clinically significant, the investigator will provide details about the action taken with respect to the test drug and about the patient's outcome.

6.1.1.2 Hospitalizations

Hospitalizations or prolonged hospitalization for the following reasons do not require reporting:

- Technical, practical, or social reasons, in absence of an AE
- Routine treatment or monitoring of the studied indication not associated with any deterioration in condition, including scheduled therapy or standard procedure for the target disease of the study, and those required to allow efficacy measurement for the study
- Diagnostic or elective surgical procedures for preexisting conditions or a procedure that is planned (e.g., planned prior to starting of treatment on study)
- Emergency outpatient treatment or observation that does not result in admission, unless fulfilling other seriousness criteria

6.2 RESPONSE CRITERIA

Response assessment will be based on three sets of response criteria: Revised Response Criteria for lymphoma by Cheson et al³⁸, also by Cheson et al³⁹, and International Consensus Meeting Criteria for ATL⁴.

6.2.1 Criteria of response for Malignant Lymphoma ⁵⁷

6.2.1.1 Complete response

The designation of a complete response (CR) requires all of the following: **(1)** Complete disappearance of all detectable clinical evidence of disease and disease-related symptoms if present before therapy; **(2)** a post-treatment residual mass is permitted as long as it is PET negative. If a pretreatment PET scan was negative, all lymph nodes and nodal masses must have regressed on CT to normal size (<1.5 cm in their greatest transverse diameter for nodes > 1.5 cm before therapy); **(3)** Previously involved nodes that were 1.1 to 1.5 cm in their long axis and more than 1.0 cm in their short axis before treatment must have decreased to < 1.0 cm in their short axis after treatment; **(4)** The spleen and/or liver if considered enlarged before therapy based on a physical examination or CT scan, should not be palpable on physical examination and should be considered normal size by imaging studies, and **(5)** If the bone

marrow was involved by lymphoma before treatment the infiltrate must have cleared on repeat bone marrow biopsy.

6.2.1.2 Partial response

The designation of a partial response (PR) requires all of the following: **(1)** At least a 50% reduction in the sum of the product of the diameters of up to six of the largest dominant nodes or nodal masses. These nodes or masses should be selected according to all of the following: they should be clearly measurable in at least two perpendicular dimensions; if possible they should be from disparate regions of the body; and they should include mediastinal and retroperitoneal areas of disease whenever these sites are involved; **(2)** No increase in the size of other nodes, liver, or spleen; **(3)** Splenic and hepatic nodules must regress by >50% in their SPD or for single nodules in the greatest transverse diameter; **(4)** With the exception of splenic and hepatic nodules, involvement of other organs is usually assessable and no measurable disease should be present. Bone marrow assessment is irrelevant for determination of a PR if the sample was positive before treatment. Patients who achieve a CR by the above criteria but who have persistent morphologic bone marrow involvement will be considered partial responders; **(5)** No new sites of disease; **(6)** If the pretreatment PET scan was positive, the post-treatment PET should be positive in at least one previously involved site; and **(7)** If a pretreatment PET was negative, CT criteria should be used.

6.2.1.3 Stable disease

A patient is considered to have stable disease (SD) when he or she fails to attain the criteria needed for a CR or PR, but does not fulfill those for progressive disease. The PET should be positive at prior sites of disease with no new areas of involvement on the post treatment CT or PET. If the pretreatment PET was negative, there must be no change in the size of the previous lesions on the post treatment CT scan.

6.2.1.4 Progressive disease

Lymph nodes should be considered abnormal if the long axis is more than 1.5 cm regardless of the short axis. If a lymph node has a long axis of 1.1 to 1.5 cm, it should only be considered abnormal if its short axis is more than 1.0 cm. Lymph nodes < 1.0 X < 1.0 cm will not be considered as abnormal for relapse or progressive disease. Other criteria for progressive disease include the following: **(1)** Appearance of any new lesion more than 1.5 cm in any axis during or at the end of therapy, even if other lesions are decreasing in size. Increased FDG uptake in a previously unaffected site should only be considered relapsed or progressive disease after confirmation with other modalities. **(2)** At least a 50% increase from nadir in the sum of the products of the diameters of any previously involved nodes, or in a single involved node, or the size of other lesions. A lymph node with a diameter of the short axis of less than 1.0 cm must increase by >50% and to a size of 1.5 X 1.5 cm or more than 1.5 cm in the long axis. **(3)** At least a 50% increase in the longest diameter of any single previously identified node more than 1 cm in its short axis; **(4)** Lesions should be PET positive if the lesion was PET positive before therapy unless the lesion is too small to be detected by PET; **(5)** Measurable extranodal disease should be assessed in a manner similar to that for nodal disease. For these recommendations, the spleen is considered nodal disease. Disease that is only assessable will be recorded as present or absent only, unless, while an abnormality is still noted by imaging studies or physical exam, it is found to be histologically negative.

6.2.2 Criteria of Response for ATL

6.2.2.1 Complete response

Complete response (CR) is defined as disappearance of all clinical, microscopic, and radiographic evidence of disease. All nodes must have regressed to normal size (1.5 cm in their greatest transverse diameter) and previously involved nodes that were 1.1 to 1.5cm must have decreased to 1.0 cm. Because HTLV-1 carriers frequently have a small percentage of abnormal lymphocytes with polylobated nuclei, so called flower cells in peripheral blood, provided that less than 5% of such cells remained and the absolute lymphocyte count, including flower cells, was less than $4 \times 10^9/L$, CR is attained.

6.2.2.2 Complete response unconfirmed

A designation of unconfirmed complete response (CRu) requires a 75% reduction in tumor size with a residual mass after treatment.

6.2.2.3 Partial response

Partial response (PR) is defined as a $\geq 50\%$ reduction in the sum of the products of the greatest diameters of measurable disease without the appearance of new lesions. In addition, a 50% or greater reduction in absolute abnormal lymphocyte counts in peripheral blood is required to attain PR.

6.2.2.4 Progressive disease

Progressive disease (PD) in peripheral blood is defined by a 50% increase from nadir in the count of flower cells and an absolute lymphocyte count, including flower cells, of $4 \times 10^9/L$.

PD or relapsed disease in the other lesions is defined as a 50% increase from nadir in the sum of the products of measurable disease or the appearance of new lesions excluding skin.

6.2.2.5 Stable disease

Stable disease is defined as failure to attain CR/PR or PD.

6.3 TOXICITY CRITERIA

The following adverse event management guidelines are intended to ensure the safety of each patient while on the study. The descriptions and grading scales found in the revised NCI Common Terminology Criteria for Adverse Events (CTCAE) version 4.0 will be utilized for AE reporting. All appropriate treatment areas should have access to a copy of the CTCAE version 4.0. A copy of the CTCAE version 4.0 can be downloaded from the CTEP web site http://ctep.cancer.gov/protocolDevelopment/electronic_applications/ctc.htm#ctc_40.

7 NIH REPORTING REQUIREMENTS / DATA AND SAFETY MONITORING

7.1 DEFINITIONS

Please refer to definitions provided in Policy 801: Reporting Research Events found [here](#).

7.2 OHSRP OFFICE OF COMPLIANCE AND TRAINING / IRB REPORTING

7.2.1 Expedited Reporting

Please refer to the reporting requirements in Policy 801: Reporting Research Events and Policy 802 Non-Compliance Human Subjects Research found [here](#).

7.2.2 IRB Requirements for PI Reporting at Continuing Review

Please refer to the reporting requirements in Policy 801: Reporting Research Events found [here](#).

7.3 NCI CLINICAL DIRECTOR REPORTING

Problems expeditiously reported to the OHSRP in iRIS will also be reported to the NCI Clinical Director. A separate submission is not necessary as reports in iRIS will be available to the Clinical Director.

In addition to those reports, all deaths that occur within 30 days after receiving a research intervention should be reported via email to the Clinical Director unless they are due to progressive disease.

To report these deaths, please send an email describing the circumstances of the death to [name] at [contact] within one business day of learning of the death.

7.4 NIH REQUIRED DATA AND SAFETY MONITORING PLAN

7.4.1 Principal Investigator/Research Team

The clinical research team will meet on approximately a weekly basis when patients are being actively treated on the trial to discuss each patient. Decisions about dose level, enrollment and dose escalation if applicable will be made based on the toxicity data from prior patients.

All data will be collected in a timely manner and reviewed by the principal investigator. Events meeting requirements for expedited reporting as described in section [7.2.1](#) will be submitted within the appropriate timelines.

The principal investigator will review adverse event and response data on each patient to ensure safety and data accuracy. The principal investigator will personally conduct or supervise the investigation and provide appropriate delegation of responsibilities to other members of the research staff.

8 STATISTICAL CONSIDERATIONS

The primary goal of this study is to evaluate the safety and efficacy of ruxolitinib in patients with smoldering or chronic adult T-cell leukemia (ATL). Despite the Shimoyama Classification system⁴, smoldering and chronic phase ATL patients appear to be a biologically heterogeneous group. Chronic ATL with adverse disease characteristics such as poorer performance status, lower neutrophil count receiving chemotherapy have been reported to have a poorer median survival than is generally expected for this subtype of ATL and this should be reflected in lower response rate to treatments. Picking an acceptable phase II target response rate can be difficult, due to the lack of clarity in the historical database for treated chronic or smoldering ATL. Survival is the clinical endpoint most often captured in these treatment reports and response rates are frequently not cited and, as previously discussed (Section [1.6](#)), survival data can be inconsistent.⁴⁷ Given the available data that indicates previously treated chronic or smoldering subtype ATL patients who are further along in the natural history of their ATL and respond less well to any form of treatment, we believe that an initial target response rate of 30% in our referral patient population is an appropriate target value for response in a phase II trial⁴¹. We will adhere strictly to the definition of chronic and smoldering subtypes as defined by Shimoyama for the enrolled patients.

Original Study Design: In this study for chronic or smoldering ATL will use an optimal two-stage Simon design to test for early evidence for efficacy based on complete and partial response. The design is based on the following: (a) the response proportion (partial and complete response) will be less than 5% if the treatment is totally ineffective ($P_0=0.05$), (b) the treatment will be considered effective and worthy of future investigation if the true response proportion $>30\%$ ($P_1=0.30$) (see Section [1.6](#)), (c) a type I error rate of 5% (i.e., the probability of concluding that the treatment is

effective if the true response rate is 5% is 0.05), (d) a power of 90% (i.e., the probability of concluding that the treatment is effective if the true response proportion is 30% is 0.95).

Updated Study Design (Amendment D): Although there were 4 responding patients in the first 12 patient who were treated, the activity was not sustained even in these patients; therefore, we are now changing the treatment regimen to evaluate the activity of augmented dosing (effective with Amendment D). We plan to treat a total of 9 patients at the MTD or MAD and will not proceed with the same original two-stage phase 2 dosing. Patients who discontinue treatment within the first 28 days for reasons other than toxicity will be considered inevaluable. In order to allow for this assessment of patients attempting higher treatment doses, the protocol will require an additional 15-21 patients. Accounting for the previously enrolled 12 subjects, the new design, and to assess up to 9 patients for response at the MTD/MAD level with the new increased dose levels as well as allowing for up to two (2) inevaluable patients: the new accrual ceiling will be set at 35 patients.

The major objective of this study continues to be to determine the antitumor activity of ruxolitinib with regard to response rate and time to progression. Response rate will be based on the number of patients who achieve either a complete or partial response to therapy. Time to progression will be measured from the date of registration until documentation of disease progression..

An exploratory analysis will be performed in the two subgroups of patients defined by the inhibition of their pretreatment *in vitro* ATL cells proliferation by ruxolitinib treatment. The patients will be distinguished on the basis of the results of a 6-day *ex vivo* culture analyses performed on patient peripheral blood mononuclear cells prior to drug administration. One subgroup of patients will be defined as those who fulfill the following criteria: peripheral blood mononuclear cells proliferate *ex vivo* ($\geq 5,000$ CPM/1 μ C) in 6-day culture and their thymidine uptake must be reduced by 40% by the addition of 10 μ M ruxolitinib. The other group of patients would be all the remaining treated patients that do not fulfill these criteria. Since a limited number of patient samples have been assessed to date, it is not clear what percentage of smoldering or chronic stage ATL patients will fulfill the criteria for group 1.

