1 INTRODUCTION

1.1 STUDY OBJECTIVES

1.1.1 Primary Objective

- To determine the maximum tolerated dose and clinical response rate for ruxolitinib given at doses of 30, 40 or 50 mg orally twice daily in patients with smoldering, chronic and biologically indolent acute or lymphomatous subtype of ATL

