2.3.1.2 Arms

Number	Name	Description
1	Experimental Treatment (CLOSED)	Ruxolitinib 20mg orally twice daily for 28 days. Patient may continue to receive treatment until PD.
2	Experimental Treatment – Dose Escalation	Ruxolitinib 30-50 mg orally twice daily for 28 days to determine the maximum tolerated dose (MTD). Patients may continue to receive treatment until PD or unacceptable toxicity.
3	Experimental Treatment – Dose Expansion	Ruxolitinib at the MTD orally twice daily for 28 days. Patients may continue to receive treatment until PD or unacceptable toxicity.

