3.1.2 Dose Escalation

Dose escalation will proceed in cohorts of 3-6 patients. The MTD is the dose level at which no more than 1 of up to 6 patients experience DLT during the first cycle (28 days) treatment, and the dose below that at which at least 2 (of \leq 6) patients have DLT as a result of the drug. If a patient did not experience DLT and did not finish treatment, he or she will not be evaluable for toxicity and will be replaced in the dose level.

Dose Escalation Schedule	
Dose Level	Dose of Ruxolitinib
Level 1	30 mg PO BID
Level 2	40 mg PO BID
Level 3	50 mg PO BID

Dose escalation will follow the rules outlined in the table below; this study plans to treat 9 patients at the MTD/MAD:

Number of Patients with DLT at a Given Dose Level	Escalation Decision Rule
0 out of 3	Enter up to 3 patients at the next dose level
≥ 2	Dose escalation will be stopped. This dose level will be declared the maximally administered dose (highest dose administered). Up to three (3) additional patients will be entered at the next lowest dose level if only 3 patients were treated previously at that dose.
1 out of 3	Enter up to 3 more patients at this dose level. 
• If 0 of these 3 patients experience DLT, proceed to the next dose level.• If 1 or more of this group suffer DLT, then dose escalation is stopped, and this dose is declared the maximally administered dose. UP to three (3) additional patients will be entered at the next lowest dose level if only 3 patients were treated previously at that dose.
≤ 1 out of 6	This is the MTD and is generally the recommended phase 2 dose. NOTE: If ≤ 1 out of 6 patients with DLT occurs at DL3, the MTD will not have been identified and DL3 will be declared the MAD for further study.

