Patients who come off treatment for a reason other than disease progression, will continue to be followed until progression (or another off-study reason per Section 3.8.2). Assessments may be done at NIH or outside, with optional imaging at the timing discretion of the investigator.

3.4.1.6 **FACS panel restaging for response:** These samples will be collected at: pre-treatment; on day 15 and pre-cycle 2 and 3 (if feasible); at the same time as disease restaging occurs; and, at the end of treatment and off study evaluations (if appropriate). The multicolor FACS panel listed below in **Table 4** will be performed to determine percentage and absolute number of CD3^{dim} CD4⁺ ATL. Changes in CD4⁺ CD8⁺, NK cells and T-cell central and effector memory subsets will also be assessed in these analyses (see Section 5.1.3). Additional tubes or cell surface

markers maybe inserted or substituted into this panel later during the conduct of the trial without increasing the amount of blood sampled. **NOTE:** In case of scheduling conflicts, TBNK may be substituted.

Table 4: FACS panel surface markers and fluorokine

Tube	FITC	PE	PerCP	PE-Cy7	APC	APC-eFluor 780
1	CD14					CD45 Ungated
2	IgG	IgG	IgG	IgG	IgG	CD45
3	CD45RA	CD62L	CD4	CD3	CD8	CD45
4	CD7	CD25	CD4	CD3	CD8	CD45
5	CD3/CD16+CD56		CD20			CD45
6	CD2	IL15R α	CD4	CD3		CD45
7	CD57	MIK β 3	CD127	CD3	CD4	CD45
Initial Study Only						
8	CD3	CD25	CD194(CCR4)		CD4	CD45

3.4.1.7 Hepatitis B serologies and quantitative DNA: These will be repeated for patients with indolent hepatitis B infections every 3-4 months during treatment as indicated in Section [3.5 Study Calendar](#); and, at least yearly after treatment.

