3.8.1 Off-Treatment Criteria

- Unacceptable toxicity as defined in Section [3.1.3](#) or [3.3](#)
- Disease progression not responsive to highest dose level that can be safely administered
- Persistent (> 14 days) treatment-related adverse events \geq grade 2
- Investigator discretion
- Positive pregnancy test

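### Section 8 makes every patient who stops within 28 days for a non-toxicity reason inevaluable, with no exception for progression, so early progressors most naturally drop out of the response denominator

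*Combined protocol and SAP*

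**What the plan says.** The primary objective in Section 1.1.1 is "To determine the maximum tolerated dose and clinical response rate for ruxolitinib" at the three escalated dose levels, so the response rate is a primary quantity.

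Section 8, under the Amendment D design, plans 9 patients at the MTD or MAD and then gives the evaluability rule: "Patients who discontinue treatment within the first 28 days for reasons other than toxicity will be considered inevaluable". The same paragraph explains the accrual ceiling as covering the 12 earlier patients and the new design, "to assess up to 9 patients for response at the MTD/MAD level", "as well as allowing for up to two (2) inevaluable patients: the new accrual ceiling will be set at 35 patients". The next paragraph defines response rate by its numerator, complete plus partial responses. It gives no denominator.

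Evaluability for toxicity is handled separately in Section 3.1.2. Of a patient who has no DLT and does not finish treatment, it says "he or she will not be evaluable for toxicity and will be replaced in the dose level".

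Progression is a reason for stopping distinct from toxicity. For the escalation and expansion arms, Section 2.3.1.2 says "Patients may continue to receive treatment until PD or unacceptable toxicity". Section 3.8.1 lists "Disease progression not responsive to highest dose level that can be safely administered" as its own criterion, apart from unacceptable toxicity.

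**The concern.** The 28-day rule sorts patients by when and why they stopped, and toxicity is the only reason that keeps a patient evaluable. Someone whose disease worsens and who stops by day 28 is a treatment failure, yet meets the rule for being set aside. If that means removal from the response analysis, the exclusion depends on the outcome being measured. It takes away only non-responders, so it moves the response rate upward whenever at least one other patient responds. That is a bias, not merely a loss of precision.

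Amendment D attaches no success threshold to the 9 patients. What is at stake is therefore an overstated descriptive rate, not an altered go/no-go decision. Early stops unrelated to disease, such as withdrawal or non-compliance, are excluded as well; the direction of their effect is unknown.

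**Working it through.** **1. Reproduce the plan's own figure.** Section 8 gives 12 earlier patients, 15–21 additional patients and an allowance of 2 inevaluable patients. At the upper end, 12 + 21 + 2 = 35, which matches the stated ceiling. New patients number at most 35 − 12 = 23, and the allowance of 2 belongs to that whole group.

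**2. Can a patient fall under the rule through progression?** Yes. Sections 2.3.1.2, 3.1.1 and 3.8.1 all make progression a ground for stopping that is separate from toxicity. Scheduled restaging after cycle 1 is on day 29, but the cycle 1 window is ±2 days (Sections 3.4.1 and 3.5). Sections 3.4.1.5 and 3.4.1.10 also allow unscheduled assessment for suspected progression.

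**3. Does any other text count such a patient as a non-responder?** None was found. Section 6.2 defines progressive disease but does not set the analysis denominator. The day-15 FACS sample in Section 3.4.1.6 does not help, because the rule applies whatever that sample shows.

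**4. Effect on an observed rate.** Take 3 responders as an illustration, since this lies near the 30% target of the original design. Intervals are exact (Clopper-Pearson) 95%. Section 8 does not say whether its inevaluable patients are replaced; Section 3.1.2 does replace them for toxicity. Both cases are shown.

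| Early progressors at the MTD/MAD | Excluded (rule as written) | Counted as non-responders |
|---|---|---|
| 1, replaced | 3/9 = 33.3% (7.5–70.1%) | 3/10 = 30.0% (6.7–65.2%) |
| 2, replaced | 3/9 = 33.3% (7.5–70.1%) | 3/11 = 27.3% (6.0–61.0%) |
| 1 of 9, not replaced | 3/8 = 37.5% (8.5–75.5%) | 3/9 = 33.3% (7.5–70.1%) |
| 2 of 9, not replaced | 3/7 = 42.9% (9.9–81.6%) | 3/9 = 33.3% (7.5–70.1%) |

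**5. Effect on the expected rate.** Let p be the true response rate among all treated patients and e the share who progress and stop by day 28, none of whom respond. Excluding them gives an apparent rate of p / (1 − e). The documents give no value for e, so every non-zero value below is an assumption.

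| e | True 20% appears as | True 30% appears as |
|---|---|---|
| 0 | 20.0% | 30.0% |
| 1/23 = 4.3% (one among all new patients) | 0.20 × 23/22 = 20.9% | 0.30 × 23/22 = 31.4% |
| 2/23 = 8.7% (two among all new patients) | 0.20 × 23/21 = 21.9% | 0.30 × 23/21 = 32.9% |
| 2/11 = 18.2% (both at the MTD/MAD, replaced) | 0.20 × 11/9 = 24.4% | 0.30 × 11/9 = 36.7% |

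**The case against.** The strongest counter-argument is that the sentence only restates the DLT rule. Its 28 days are the DLT window, and keeping toxicity stops while setting other early stops aside is ordinary DLT logic. The allowance of two covers the whole escalation, not only the response patients. This reading is possible, and the response denominator is indeed inferred rather than written. But Section 3.1.2 already covers toxicity, and the Section 8 paragraph places the allowance beside the patients assessed for response. If DLT evaluability alone was meant, Section 8 does not say so, and the same edit is needed.

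Second, progressive disease is a response category in Section 6.2, so a documented progressor has arguably been assessed. That makes exclusion less certain, but it does not override an explicit rule with no exception for progression.

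Third, early progression should be uncommon. Eligibility selects smoldering, chronic or clinically indolent disease and excludes short life expectancy, and the first scheduled restaging falls at the end of cycle 1. This stands as a limit on size. The pooled 1/23 and 2/23 figures also span three dose levels, whereas the response assessment concerns the 9 patients at the MTD/MAD.

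Fourth, with 9 patients, no decision rule and wide intervals, a reader could spot each early progressor individually. That lowers the stakes, but it is no reason to leave an avoidable one-directional bias in a primary-objective estimate. On time to progression, the definition already runs from registration to documented progression, so a sentence on that endpoint is a clarification only.

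**Conclusion.** The concern holds and should be fixed. As written, the rule makes progressors who stop by day 28 inevaluable, and no other text restores them as non-responders. Confidence is medium, because the application to the response denominator rests on context.

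The size rests on an unknown early-progression rate. It is zero if nobody progresses and stops by day 28. With replacement, one or two such patients at the MTD/MAD shift an illustrative result by 3.3 or 6.1 percentage points (33.3% against 30.0% or 27.3%). In the second case the estimate moves from below to above the original 30% target, which no longer serves as a criterion. Without replacement, two early progressors among 9 give a larger gap: 42.9% against 33.3%, or 9.5 points (3/7 − 3/9). All these shifts are small beside the exact confidence intervals.

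**What to change.** In Section 8:

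- State that the 28-day inevaluable rule applies to DLT/MTD evaluability only.
- Report response in all patients treated at the MTD/MAD with an exact confidence interval, counting progression or death from disease before the first response assessment as non-response.
- Confirm that early progression is an event for time to progression, since the text does not say whether the 28-day rule affects that endpoint.
- Give the evaluable-only rate, and the handling of early stops unrelated to disease, as a sensitivity analysis.

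The cost is two or three sentences, with no extra patients or procedures. The reported response rate may be slightly lower.
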